### 9.2 Adverse Events

AEs will be recorded and evaluated for their seriousness, severity, and relationship to the study medication. Adverse events will be collected and documented during the course of the study,

from ICF signature until a period of  $12\pm 2$  days following the last study drug administration, and they will be followed-up until complete resolution, or until the Investigator judges it to be safe to discontinue follow-up.

Treatment-emergent AEs and non-TEAEs (those occurring prior to administration of study medication or that first occurred prior to study drug administration and did not worsen in frequency or severity) will be listed. TEAEs will be defined as AEs that occur on or after the date and time of study drug administration, or those that first occur pre-dose but worsen by increase in occurrence or severity after study drug administration.

The incidence of TEAEs will be summarized using the safety population. The updated version of MedDRA® dictionary will be used to classify all AEs reported during the study by SOC and PT.

Incidence of subjects who experienced TEAEs will be presented by treatment and overall, SOC, PT, by Investigator-assessed relationship and also by severity. Each subject may only contribute once to each of the incidence rates, for a TEAE following a given treatment, regardless of the number of occurrences; the highest severity or highest relationship will be presented, as appropriate. In each table, SOC will be presented in descending order of overall incidence rate in terms of frequency of subjects and then in frequency of events (alphabetical order will be used in case of equal rates). For each SOC, PT will be presented the same way.

Incidence of TEAEs (number of events) will also be presented by treatment and overall, by SOC, and PT, by Investigator-assessed relationship and severity.

Frequency of subjects experiencing Serious Treatment Emergent Adverse Events and Suspected Unexpected Serious Adverse Drug Reactions; and the number of events would be also summarized per treatment and overall. Also, these events and Serious Adverse Events will be listed per subject.

The severity of AEs will be assessed and graded according to the most recently published National Cancer Institute Common Terminology Criteria for AE (CTCAE).

The relationship of an AE or SAE to the study drug will be assessed according to the study protocol as:

- Related to study drug;
- Not related to study drug;
- Unknown.

The assessment of the relationship of an adverse event with the administration of study drug is a clinical decision based on all available information at the time of the completion of the CRF.

- An assessment of "Related" indicates that there is a reasonable suspicion that the AE is associated with the use of the study drug.
- An assessment of "Not related" would include the existence of a clear alternative explanation, or non-plausibility.

Page 23 of 44

• An assessment "Unknown" indicates there is not a reasonable suspicion that the AE is associated with the use of the study drug and at the same time there is not the existence of a clear alternative explanation or non-plausibility. In this case, Investigator has to collect all possible information in order to assess the relationship with the study drug, particularly in case of SAEs.

### 9.2.1 Adverse Events of Special Interest

Adverse events of special interest (AESIs) for this study will include the following:

- Torsade de pointes;
- Sudden death;
- Ventricular tachycardia;
- Ventricular fibrillation and flutter;
- Post-dose syncope ;
- Seizures.

Which are to be classified as AESI in the CRF and will be recorded from ICF signature and throughout the study period until study completion. When these events are identified they should be examined closely for other risks factors, and evaluated. Also the need for evaluation by a cardiac specialist will be discussed by the Investigator and the Sponsor.

Incidence of AESIs (number of events) will also be presented by treatment and overall for severity and relationship and by treatment and overall for age, gender, pre-existing cardiac disease, electrolyte disturbances and concomitant medications.

### 9.3 Laboratory Parameters

Clinical laboratory (hematology, biochemistry, coagulation [PT and PTT], and urinalysis) results will be obtained at screening, before dosing of each period (at check-in or in the morning of Day -1), 24 (Day 2) and 72 (Day 4) hours post-dose, and at study exit.

Hematology parameters include the following: complete blood count with differential, hemoglobin, and hematocrit.

Biochemistry parameters include the following: cholesterol (total, low-density lipoprotein [LDL] and high-density lipoprotein [HDL]), triglycerides, albumin, alkaline phosphatase, aspartate aminotransferase [AST], alanine aminotransferase [ALT], urea, cystatin C, calcium, chloride, glucose, phosphorus, potassium, creatinine, sodium, total bilirubin, and total protein.

Coagulation parameters include the following: PT and PTT.

Urinalysis parameters include the following: macroscopic examination, pH, specific gravity, protein, glucose, ketones, bilirubin, occult blood, nitrite, urobilinogen, and leukocytes. Unless otherwise specified, microscopic examination will be performed on abnormal findings.

Human Immunodeficiency Virus (HIV) antigen and antibody, Hepatitis B surface antigen (HBsAg), and Hepatitis C (HCV) antibody detection will be performed at screening.

A urine pregnancy test will be performed at screening and at study exit, and a serum pregnancy test will be performed at check-in of each period.

A urine drug screen (amphetamines, methamphetamines, barbiturates, benzodiazepines, tetrahydrocannabinol, cocaine, opiates, phencyclidine [PCP], 3,4-methylenedioxymethamphetamine [MDMA], methadone), an alcohol breath test, and a urine cotinine test, will be performed at screening. A urine drug screen, an alcohol breath test, and a urine cotinine test and will also be performed before dosing of each period.

Listings of all clinical laboratory results will be provided with the abnormal values flagged with "L" (below normal) and "H" (above normal) for continuous parameters, and "A" (abnormal) for categorical parameters, including the evaluation of the abnormal result as clinically significant or not clinically significant.

Clinically significant laboratory abnormalities will be recorded as AEs or SAEs and identified as Grade 3 to 4 laboratory test results graded according to numeric laboratory test criteria in the latest version of Common Technical Criteria for Adverse Events (CTCAE version 5.0) if available, otherwise according to the latest version of Division of AIDS (DAIDS) Table for Grading the Severity of Adult and Pediatric Adverse Events Corrected will be provided.

Descriptive statistics (mean, median, SD, Min, Max, and sample size) for each clinical laboratory test (continuous variables) will be presented by treatment and overall. Change from baseline for hematology, biochemistry, coagulation, and urinalysis will be presented. Baseline is defined as the last assessment prior to dosing with study drug in that same treatment period (i.e. baseline measurements must have been collected prior to administration of study drug in that treatment period). The unscheduled results will not be included in the summary tables. The repeated laboratory test performed due to safety reasons, after a clinically significant abnormal results is obtained, will be considered as follow-up and analyzed as such. For categorical variable (urinalysis test), the number of subjects (frequency and percentage) will be tabulated by results (e.g., negative, positive, trace ...). A summary table of shifts from baseline to study exit will be provided. Results from repeat tests will not be included in the summary statistics unless the repeat was required (and documented as such) due to technical reasons or an invalid initial result.

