### 9.4 Vital Signs

Blood pressure (BP), heart rate (HR), respiratory rate (RR), and oral temperature (OT) will be measured in a supine position at: screening, pre-dose, and approximately 2, 3, 6, 12, and 24 hours post-dose for each period, and at study exit. Vital signs will be matched to the safety ECG (at screening, pre-dose, and approximately 2, 3, 6, 12, and 24 hours post-dose for each period, and at study exit). When vital signs measurements coincide with ECG or blood draw, the assessments will be performed in the following order: ECG, vital signs, and blood draw. Urine collection timepoints will not be prioritized over safety and other PK assessments.

Italfarmaco S.p.A.

For the measurement of BP, 2 measures performed after at least 5 minutes of resting in supine position should be taken 2 minutes apart from each other.

Descriptive statistics (mean, median, SD, Min, Max, and sample size) will be presented overall for baseline and study exit and by the associated current treatment for on-study measurements and for each vital sign measurement. Descriptive statistics for change from baseline to study exit for on-study measurements will also be presented. Baseline will be defined as the last results (scheduled or unscheduled) obtained prior to drug administration in each period. Unscheduled results will not be included in the summary tables otherwise. Results from post-dose repeat tests will not be included in the summary statistics unless the repeat was required (and documented as such) due to technical reasons or an invalid initial result.

A table summarizing the descriptive statistics, a table showing shift of results (low, normal and high) from baseline to post dose and a listing of all vital signs results will be provided.

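### SAP 9.3's only laboratory shift table runs to study exit, so it cannot count, dose by dose and within subject, how many subjects moved from normal to abnormal

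*SAP*

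**What the plan says.** SAP 9.3 (Laboratory Parameters) names a single shift table: "A summary table of shifts from baseline to study exit will be provided". The sentence comes directly after the one on urinalysis categories: "For categorical variable (urinalysis test), the number of subjects (frequency and percentage) will be tabulated by results". The same section sets baseline by period: "Baseline is defined as the last assessment prior to dosing with study drug in that same treatment period".

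Protocol 9.11 and footnote 1 of the Schedule of Events make the Period 4 Day 4 procedures the study exit for completers. Subjects who leave early have one exit visit, within 14 days of last participation. SAP 9.3 schedules laboratory tests at check-in and at 24 h and 72 h after dosing in every period.

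The other planned laboratory output is:

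- descriptive statistics by treatment and overall, including minimum and maximum, for each continuous test, together with change from baseline (SAP 9.3);
- listings of all results, with values outside the normal range flagged and their clinical significance given (SAP 9.3);
- clinically significant abnormalities recorded as adverse events and "identified as Grade 3 to 4 laboratory test results" (SAP 9.3), then summarised by treatment under SAP 9.2.

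On extra samples, SAP 9.3 says "The unscheduled results will not be included in the summary tables", and that safety repeats after a clinically significant result "will be considered as follow-up and analyzed as such". For vital signs, SAP 9.4 plans "a table showing shift of results (low, normal and high) from baseline to post dose"; SAP 9.5 plans a similar table for the safety ECG.

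**The concern.** In this four-period crossover every completer receives 100 mg, 300 mg, placebo and moxifloxacin, with laboratory sampling after each. A shift table is useful because it counts the subjects who start a period normal and become abnormal on a given treatment. Means, minima and maxima do not give that count. A table that ends at study exit gives it for one treatment per subject, so it becomes a small parallel-group comparison of whichever treatment came last.

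The case where this matters most is haematology. Protocol 9.15.1 asks for careful monitoring of haematological parameters and singles out platelets, and exclusion criterion 5 sets platelet and neutrophil limits. Evaluating the safety and tolerability of the two doses is a secondary objective. A mild, dose-related fall in platelets that no one judges clinically significant would not reach the adverse event tables, and the planned summaries would not say how many subjects it affected at each dose.

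**Working it through.** The documents give no figure for the shift table, so there is none to reproduce. The check counts what the table can contain.

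**1. Which samples enter.** Each subject has one exit. With the period-specific baseline, a completer's shift runs from the last sample before dosing in Period 4 to Period 4 Day 4. Taking a Period 1 baseline instead would not help, because the shift would then span all four treatments.

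**2. Share of draws.** Scheduled post-dose draws per completer: 2 (24 h and 72 h) × 4 periods = 8. The exit table uses 1, and 1/8 = 12.5%. With 28 completers this is 28 of 28 × 8 = 224 draws. For each treatment it is 7 of 2 × 28 = 56.

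**3. Subjects per treatment.** The Period 4 treatments for sequences 1 to 12 (Protocol 9.4; SAP 3.6, Table 1) are M, P, ST, T, M, T, P, ST, M, ST, T, P. Each treatment is last in 3 of 12 sequences (25%). With equal allocation, 0.25 × 28 = 7 subjects per treatment, or 0.25 × 34 = 8.5. If blocks of 12 are filled in order (an assumption), the range is 6 to 9 of 28, or 7 to 9 of 34.

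**4. Within-subject pairs.** Subjects contributing to both 300 mg and placebo: 0 in the exit table, against up to 28 (or 34) in a per-period table.

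**5. What the exit table alone could show.** If no shift is seen on a treatment, the one-sided 95% upper bound on the shift rate is 1 − 0.05^(1/n):

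| n | Upper bound |
|---|---|
| 7 | 34.8% |
| 8 | 31.2% |
| 9 | 28.3% |
| 28 | 10.1% |
| 34 | 8.4% |

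The documents give no shift rate. For assumed true rates p, the chance of counting at least one shift is 1 − (1 − p)^n:

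| Assumed p | n = 7 (exit table) | n = 28 (per-period table) |
|---|---|---|
| 5% | 30.2% | 76.2% |
| 10% | 52.2% | 94.8% |
| 20% | 79.0% | 99.8% |

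The figures in step 5 describe the exit table taken alone. They are not the trial's ability to notice an abnormal value, which also rests on the other outputs listed above.

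**6. The urinalysis-only reading.** If the shift sentence belongs to the urinalysis sentence before it, steps 2 to 5 apply to urinalysis, and the SAP text plans no shift table for platelets or neutrophils.

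**The case against.** The strongest reply is that nothing is lost and no commitment is broken. The protocol promises no shift table. It promises changes from baseline tabulated by study treatment (Protocol 12.4.3), and SAP sections 9 and 9.3 provide by-treatment summaries and change from baseline. A low platelet count on 300 mg at any scheduled draw is reflected in that treatment's minimum and is flagged in the listings, from which the count per dose could be made by hand. Abnormalities judged clinically significant become adverse events. The exit table may be meant only as an end-of-study summary; for vital signs, SAP 9.4 itself separates exit data from on-study data by treatment. All of this stands, and it limits the point to a missing count.

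Three stronger readings are tempting, and the documents do not support them.

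- A reader might infer that a dose-related laboratory effect could go unseen, or that the 30% to 79% figures are the trial's detection chances. The by-treatment minima and maxima and the flagged listings cover all scheduled draws, so they are not.
- A reader might infer that the vital-sign and safety-ECG shift tables are equally unsuitable, or are not split by treatment. SAP 9.4 and 9.5 list the post-dose times (2, 3, 6, 12 and 24 h). SAP section 9 gives by-treatment summaries of vital signs, and Protocol 12.4.3 gives by-treatment changes for ECG as well. What is unstated is which post-dose value enters the shift. That is a detail which the separate table shells (SAP section 1), not available for this review, may settle.
- A reader might infer that leaving unscheduled results out (in SAP 9.4, "Unscheduled results will not be included in the summary tables otherwise") is an error. It is a stated choice with a reason: subjects with abnormal values are retested more often, so including those results makes worst values depend on how often a subject is tested. The number of results affected is unknown and may be zero.

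The urinalysis-only reading does not answer the point. It replaces a poorly suited haematology shift table with none.

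**Conclusion.** The point holds in a limited form and is minor. As written, the one laboratory shift table does not suit a crossover. It rests on 12.5% of the scheduled post-dose draws and about 7 of 28 subjects per treatment, with no within-subject contrast between either dose and placebo. If it is urinalysis-only, haematology has no shift table in the SAP text. The loss is the tabulated number of subjects per dose who moved from normal to abnormal, mainly for results not judged clinically significant. The underlying data and the other by-treatment summaries are intact.

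The sizes assume completers with all scheduled draws, equal allocation across sequences and the period-specific baseline. The 5%, 10% and 20% shift rates are illustrations. The judgement concerns the SAP text only. The primary concentration-QTc analysis and the Holter outlier analysis (SAP 10.6) are unaffected.

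**What to change.** In SAP 9.3, add to or replace the exit table with a shift table by treatment, from each period's baseline to the worst of that period's 24 h and 72 h results, at least for platelets and neutrophils. With 28 completers this gives 28 subjects under each treatment.

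Close the window at the 72 h draw. If it ran to the next dose, the following period's Day -1 sample would count both as an outcome of the earlier treatment and as the next baseline. Periods 1 to 3 would also have three scheduled draws against two in Period 4.

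Unscheduled or repeat results within the same 72 h may be added in a sensitivity version, with a footnote that subjects with abnormal values are retested more often. Keep the scheduled-only summaries. State which tests the exit table covers.

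Two editorial clarifications can go in at the same time: which post-dose value the SAP 9.4 and 9.5 shift tables use, and how results treated as follow-up in 9.3 are analysed.

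The cost is a few sentences and a few descriptive tables from data already collected.

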### 9.4 Vital Signs

Blood pressure (BP), heart rate (HR), respiratory rate (RR), and oral temperature (OT) will be measured in a supine position at: screening, pre-dose, and approximately 2, 3, 6, 12, and 24 hours post-dose for each period, and at study exit. Vital signs will be matched to the safety ECG (at screening, pre-dose, and approximately 2, 3, 6, 12, and 24 hours post-dose for each period, and at study exit). When vital signs measurements coincide with ECG or blood draw, the assessments will be performed in the following order: ECG, vital signs, and blood draw. Urine collection timepoints will not be prioritized over safety and other PK assessments.

Italfarmaco S.p.A.

For the measurement of BP, 2 measures performed after at least 5 minutes of resting in supine position should be taken 2 minutes apart from each other.

Descriptive statistics (mean, median, SD, Min, Max, and sample size) will be presented overall for baseline and study exit and by the associated current treatment for on-study measurements and for each vital sign measurement. Descriptive statistics for change from baseline to study exit for on-study measurements will also be presented. Baseline will be defined as the last results (scheduled or unscheduled) obtained prior to drug administration in each period. Unscheduled results will not be included in the summary tables otherwise. Results from post-dose repeat tests will not be included in the summary statistics unless the repeat was required (and documented as such) due to technical reasons or an invalid initial result.

A table summarizing the descriptive statistics, a table showing shift of results (low, normal and high) from baseline to post dose and a listing of all vital signs results will be provided.

### 9.5 12-Lead Safety ECG

Supine 12-lead ECG will be performed at screening (triplicate ECG will be performed at screening. The averaged value of three QTc will be included in STDM), pre-dose, and approximately 2, 3, 6, 12, and 24 hours post-dose for each period and at study exit. Safety ECG will be matched to vital signs (at screening, pre-dose, and 2, 3, 6, 12, and 24 hours post-dose for each period, and at study exit). When ECG coincides with vital signs measurements or blood draw, the assessments will be performed in the following order: ECG, vital signs, and blood draw. Urine collection timepoints will not be prioritized over safety and other PK assessments

The standard ECG parameters will be measured, including ventricular heart rate (VR), PR interval, QRS interval, QT interval, QTcB interval (Bazett's formula correction), and QTcF interval (Fridericia's formula correction). The QTcF interval will be used for clinical evaluations.

A table summarizing the descriptive statistics, a table showing shift of results (normal, abnormal non-significant (NCS) and abnormal clinically significant (CS)) from baseline to post dose and a listing of all ECG results will be presented.

#### Italfarmaco S.p.A.

#### 10. Cardiodynamic ECG Assessment

### 10.1 ECG and Pharmacokinetic Sample Collection

The cardiodynamic assessment will be performed through 12-lead ECGs extracted from continuous recordings at prespecified time points, paired with PK samples.

Continuous 12-lead ECG recordings will be performed from 1 hour prior to dosing in each treatment period to 36 hours post-dose. At the ECG core laboratory, up to 10 replicate ECGs will be extracted at each of the following time points on Day 1 in each treatment period: 3 time points prior to dosing (-45, -30, and -15 minutes) and 0.5, 1, 1.5, 2, 2.5, 3, 3.5, 4, 5, 6, 7, 8, 12, 24, and 36 hours post-dose.

Subjects will be supinely resting for at least 10 minutes prior to and 5 minutes after each time point for ECG extractions, whenever possible. Subjects will be required to avoid postural changes during these ECG recordings.

The 12-lead Holter and ECG equipment will be supplied and supported by ERT. All ECG data will be collected using Global Instrumentation (Manlius, NY, USA) Ml2R ECG continuous 12-lead digital recorder. The continuous 12-lead digital ECG data will be stored onto SD memory cards. 12-lead ECGs will be extracted from the continuous recordings at pre-determined time points as defined in the study protocol, and will be measured centrally by ERT.

ECG intervals will be measured by the core laboratory in a blinded manner using the Early Precision QT technique (EPQT) (see Appendix A for more details). The ECG database will be locked before any statistical analysis is undertaken.

Blood samples for PK determination will be drawn at the same time points in each period (i.e., pre-dose and 0.5, 1, 1.5, 2, 2.5, 3, 3.5, 4, 5, 6, 7, 8, 12, 24, and 36 hours post-dose) immediately after the ECG extractions and additionally at 48, 60, and 72 hours post-dose. ITF2357 plasma levels will be of interest to correlate with pharmacodynamic effect. Therefore, only blood samples for study treatments ITF2357 and moxifloxacin will be analyzed. Samples from subjects in the placebo treatment will be saved for analysis if needed. ITF2357 will be analyzed in all subjects, however, ITF2374, ITF2375, ITF2440, ITF2563 and ITF2955 glucuronide will only be analyzed in a subgroup of 12 evaluable subjects (the same population for whom urine samples will be analyzed) as no effect from the metabolites is expected on the QTc results. The samples that would not be analyzed will be kept frozen until bioanalysis results are obtained, if within these results any indication of a possible effect is found, all samples would be further studied.

